- Describe the criteria that define who will be included or excluded in your final study sample.

Aim 1: The final study sample will include 200 women randomized into 1 of 2 arms: Intervention (MomZing, n=100) or Control (Usual Care, n=100).

Women will be considered eligible if they:

- Are English-speaking and between the ages of 18 and 45
- Had prenatal care at KPNC and delivered their child at a KPNC hospital
- Are at increased risk of PPD between 2 and 6 months postpartuma
- Own a smartphone, computer, or TV with internet access
- Do not have a depression diagnosis or receive any treatment for depression (e.g. taken antidepressant medications or received psychotherapy)
- Are free of a heart condition and a physician recommending medically supervised physical activity
- Do not have chest pain during physical activity, or developed chest pain within the prior month
- Do not take medication for hypertension or a heart condition
- Have no tendency to fall due to syncope or dizziness
- Have no orthopedic problems that might be aggravated by physical activity
- Do not have exercise-induced asthma
- Are not pregnant or planning to become pregnant in the ensuing three months

- Have a Body Mass Index (BMI) between 18.5 and 40 (kg/m^2)
- Are not engaging in regular, moderate-to-vigorous physical activity >30 minutes per week

and if their infantsb:

- Are between 2 and 6 months old
- Weigh between 11-22 pounds
- Are free of chronic illness/disorder that prevents someone from holding or lifting them

aWomen will be considered at increased risk for PPD if they do not have a current depression diagnosis defined as a diagnosis between delivery and the time of the PHQ-9 score but have a PHQ-9 score between 10-19. Women who have a PHQ-2 score of  $\geq 3$ , administered at well-baby visits, will also be considered at increased risk.

bThe mothers in the intervention will be instructed how to safely exercise based on the infants' weight and developmental stage.

Aim 2: All clinicians and clinical leaders who are identified through the OBGYN Peripartum Depression Champions Committee, which consists of a depression champion clinician from different KPNC facilities, will be eligible to participate in the qualitative interviews.

- Describe how individuals will be screened for eligibility.

Please see above for eligibility requirements.

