- Describe the plan for disposition of information/biospecimens collected during recruitment/screening in the event of a screen failure or when a potential subject is contacted but declines participation (e.g. destroyed immediately, destroyed at end of study, retained for separate analysis or so that subjects are not contacted repeatedly about participation after they have declined, etc.).

Data collected during recruitment/screening or when a potential subject is contacted for participation but declines will be destroyed at the end of the study. Subjects will not be contacted about participation after they have declined.

Non-respondent data will be used in the study. Any collected data will be destroyed at the end of the study.

For those who decline to have their data be used for this study, any collected data will be destroyed at the end of the study.

c. Subjects Vulnerable to Coercion or Undue Influence

Indicate whether you will include or exclude each of the following special populations. Justify the inclusion of any of these populations. Describe additional safeguards to protect the rights and welfare of these subjects. Note: This refers to subjects who are known members of these populations upon enrollment or at any time during the study.

- Children

We will include children in the proposed study. We will need to access and link records for each enrolled mother/baby to extract data regarding the pregnancy and other health factors including child development and behavioral problems, maternal-infant interaction, and breastfeeding for 3 reasons: 1) inclusion/exclusion criteria (i.e. we cannot recruit women with infants that have a chronic illness and thus need to access their medical records), 2) to assess the relationships as outlined in the Aims, and 3) monitor adverse events and safety outcomes (e.g. identify any injuries that may have been treated by a doctor or required hospitalization and follow-up and their relationship with the intervention).

Only persons directly involved in the study will have access to the data identifying individual participants. Names of participants will be obtained for record-keeping purposes

only; no names will be recorded in the data analysis files. No individuals will be identified in the results of the studies. Access to computer-stored information will require simultaneous knowledge of the data format, computer language, file name, and password.

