**9. Study Procedures**

## a. Description

Describe and explain the study design, including:

- A detailed chronological description of all research procedures.

This is a hybrid effectiveness-implementation study including 1) a randomized controlled trial to test the effectiveness of MomZing to increase physical activity and reduce postpartum depressive symptoms in women at increased risk of PPD and 2) evaluation of implementation of MomZing within the KPNC health care delivery system. We will identify potential participants and assess them through clinician referrals and using KPNC's electronic health records data for eligibility. All eligible and recruited women will complete a baseline survey including self-report of PA and wear a research-grade accelerometer for 7 continuous days to assess baseline PA. We will mail the accelerometer and wearing instructions, and also provide a self-addressed prepaid postage envelope for participants to return the items after each measurement period. All participants will be informed that they do not have to answer any question in the surveys they do not wish to answer. We will then randomize 200 women into 1 of 2 arms: 1) Intervention (MomZing, n=100) or 2) Control (Usual care, n=100) using a restricted randomization scheme to ensure an acceptable level of between-arm balance in the distribution of important covariates (e.g. KP clinic, race/ethnicity, age, parity, marital status, and education). The nature of the group assignment and intervention does not allow for blinding of the treatment conditions from the participant or the research assistant whose task is to register and explain the use of the MomZing intervention. The programmer/analyst, biostatistician, and investigators will be blinded to the study arms. Once randomized, participants will begin their assigned group's intervention or control treatment for 3 months. We will obtain both self-report and accelerometer-measured PA and depressive symptoms at 3 months (T1) and 6 months (T2) post-baseline for each woman in their respective arms. There will be one final survey when the participant's child is 12 months old to assess child development. Non-respondent data will be used for those who do not respond to the recruitment emails and calls. They will be given 30 days to opt out of the study and informed that their data may be used if they do not respond.

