**Implementation evaluation measures.** Process measures and key stakeholder interviews will be used to assess the Reach, Effectiveness, Adoption, Implementation, and Maintenance components of the RE-AIM framework. *Reach* of the intervention will be evaluated using the participation rate among contacted eligible participants and comparison of characteristics available in the EHR between participants and eligible non-participants. *Effectiveness* will be measured through the results of the randomized controlled trial, by examining the data for a dose-response association between intervention engagement/adherence (number of exercise videos viewed), PA, and depressive symptoms, and through participant satisfaction with the intervention. Satisfaction will be assessed as part of the T1 online surveys. *Adoption* will be assessed by calculating personnel costs associated with the intervention (e.g. clinic referral staff). Additionally, key stakeholder interviews with clinicians and clinical leaders will address identified avenues for *adoption* of MomZing and barriers to *implementation* and *maintenance* within clinical practice at KPNC. The standard criteria for generating a RE-AIM public health impact score will be followed.

- The duration of an individual subject's participation in the study.

For the patient participants, participation will begin between 2 and 6 months postpartum (baseline), depending when they are recruited, and will conclude after the women complete the final survey when their child is 12 months old.

For the clinicians, participation is complete after the one-time interview to identify barriers and addressing implementation and evaluate potential adoption of MomZing.

- The duration anticipated to enroll all study subjects.

The anticipated duration to enroll all study subjects will be from 08/01/2020-03/31/2022.

		Year 1		Year 2		Year 3	
IRB approval		M					
MomZing development/final product		D					D
Clinic implementation workflow/protocol		D					D
Participant recruitment						M	
Data collection							M
Stakeholder interviews		M					M
Data analysis							M
MomZing effectiveness manuscript							D
Implementation findings report							D

M=milestone, D=deliverable

- The estimated date for the investigators to complete this study (complete primary analyses)  

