 NOTE: It should be clear exactly which procedures will be conducted for the research as opposed to procedures the subjects would undergo (in the exact manner described in the protocol) even if they were not participating in the study.

The estimated date will be 12/31/2022.

- Describe procedures that will be followed when subjects withdraw from the research, including withdrawal from intervention but continued information and/or biospecimen collection.

During recruitment, participants will be informed that their participation in the study is completely voluntary and that they are free to refuse to participate in the study. Their decision whether or not to participate in the study will not affect their medical care. If they decide to participate, they are free to change their mind and discontinue participation at any time without any effect on their medical care or eligibility for future care or membership in KFHP. At any time during the study, if participants no longer want to participate or have their information used as part of the study, they must write a letter stating that they withdraw their participation and authorization and send it to the PI, [name], at which time we would remove her from the study. We will use any PHI obtained for this study before they withdraw their authorization but will not use any PHI obtained after their withdrawal.

- Describe any anticipated circumstances under which subjects could be withdrawn from the research without their consent.

Women who become pregnant during the study will be withdrawn from the study.

- Describe any procedures for orderly termination.

N/A

- If the study involves genetic testing or collection of genetic information, describe this.

N/A

- Clarify whether research involving biospecimens will (if known) or might include whole genome sequencing (i.e., sequencing of a human germline or somatic specimen with the intent to generate the genome or exome sequence of that specimen).

N/A

b. Data Analysis

Describe the data analysis plan, including:

- Statistical procedures.

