#### 14. Provisions to Monitor Data to Ensure the Safety of Subjects

This is required when research involves more than Minimal Risk to subjects.

The plan might include establishing a data monitoring committee and a plan for reporting data monitoring committee findings to the IRB and the sponsor. Describe:

- Who will monitor the study data for safety?

The PIs will review all safety data collected at the 3-month (T1) and 6-month (T2) follow-up surveys.

- The plan to periodically evaluate the data collected regarding both harms and benefits to determine whether subjects remain safe.

The PIs will review reported adverse events collected at the 3-month (T1) and 6-month (T2) follow-up surveys every 6 months during data collection.

- What data are reviewed, including safety data, untoward events, and efficacy data.

We will collect data on severe or life-threatening injury or illness that required hospitalization overnight in postpartum participants or their infants, whether adverse events were related to exercise, and whether adverse events resulted in persistent or significant disability or incapacitation.

- How the safety information will be collected (e.g., with case report forms, at study visits, by telephone calls with participants).

Adverse event information will be reported by participants as part of follow-up surveys.

- The frequency of data collection, including when safety data collection starts.

Adverse event information will be collected as part of the 3-month and 6-month follow-ups surveys.

- The frequency or periodicity of review of cumulative data.

Adverse event data will be reviewed by the PIs every 6 months during data collection.

- Criteria for taking action on monitoring findings (for instance, stopping rules, immediate suspension, reporting, protocol changes, changes to monitoring frequency or plan).

Serious adverse events are not anticipated in this study. If serious adverse events (adverse events that require hospitalization or results in a persistent or significant disability or incapacitation in the postpartum participant or her infant) are reported related to exercise, the PIs will report these events to the IRB and remove participants who experience serious adverse events from the study. The PIs will incorporate protocol changes, including increasing adverse event monitoring to include identification of hospitalization events in participants using the electronic health records on a more frequent basis (i.e. monthly).

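### Two rules take women out of the study, not just the intervention, after pregnancy or an exercise-related serious event, and the plan does not say whether outcome collection continues (minor)

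*Combined protocol and SAP*

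**What the plan says.** Section 9a (Description), on withdrawal without the participant's consent: "Women who become pregnant during the study will be withdrawn from the study". No arm or time limit is given.

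Section 14, on serious adverse events in the mother or infant that are reported as related to exercise: "the PIs will report these events to the IRB and remove participants who experience serious adverse events from the study".

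The general schedule in Section 9a obtains activity and depressive symptoms at 3 months (T1) and 6 months (T2) "post-baseline for each woman in their respective arms". Women follow their assigned "intervention or control treatment for 3 months". Participation "will conclude after the women complete the final survey when their child is 12 months old".

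Eligibility in Section 5b screens on pregnancy as follows: "Are not pregnant or planning to become pregnant in the ensuing three months". That window is three months, while outcomes run to six.

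The withdrawal prompt in Section 9a asks how the study handles a woman who leaves the intervention while data collection goes on. The answer covers only a woman who withdraws by letter: data already obtained are kept, and the study "will not use any PHI obtained after their withdrawal".

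**The concern.** Both rules are triggered after randomization and both name the study, not the intervention, as what ends. Section 9a and Section 14 do not say whether these women still receive surveys and monitors. Section 9b (Data Analysis) does not say how they enter the analysis. Staff could reasonably read the rules as ending contact, and outcomes that were never collected cannot be recovered later.

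Two features make this more than missing detail. First, the pregnancy rule goes beyond exposure to MomZing. It removes usual-care women, who have no study exercise to stop. It also removes women who conceive after T1, who are past both the eligibility window and the assigned treatment but would still lose T2. Second, the serious-event rule depends on an event being attributed to exercise, which is more likely in the exercise arm. Any loss it causes would therefore tend to fall on one side of the comparison and on women who may be doing worse.

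**Working it through.** **1. The plan's own figures (Section 9b).** Inputs: 100 per arm, 16% loss, two-sided 0.05. Power of 0.80 is stated for the activity-guideline outcome and is assumed here for PHQ-8 too.
- Remaining per arm: 100 × (1 − 0.16) = 84.
- Detectable difference: (1.960 + 0.842) × √(2/84) = 0.432 SD, or 0.435 with the t distribution. The plan states 0.43.
- Power for 43% versus 23% at 84 per arm: 79.3%. The plan states 0.80.
- With no loss (100 per arm), the detectable difference would be 0.396 SD (t: 0.398). The stated 0.43 therefore already includes the 16% allowance.

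**2. Effect of removals on power.** The documents give no pregnancy or event rate, so the counts are assumptions.
- If removals fall within the 16%, nothing changes.
- If 3 per arm come on top: 97 × 0.84 ≈ 81 remain, and the detectable difference is 0.443 SD (t).
- If 6 per arm come on top: 94 × 0.84 ≈ 79 remain, and it is 0.449 SD (t). Power for 43% versus 23% falls to 76.7%.

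**3. Bias from the pregnancy rule.** Assume equal removal in both arms and outcomes unaffected by the pregnancy. A simulation used 100 per arm, correlation 0.6 between baseline and T2, a true effect of −0.43 SD, 16% random loss, a baseline-adjusted T2 comparison and 20,000 replicates. Removing 3 or 6 women per arm changed the mean effect by −0.001 and +0.001 SD, which is simulation noise.

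**4. Bias from the serious-event rule, PHQ-8.** Assume k intervention women whose T2 score is 1 SD worse because of the event. Keeping them moves the arm mean by k/100 SD, and removing them takes that away.
- k = 1, 2, 3 gives 0.01, 0.02, 0.03 SD in favour of the intervention.
- The same simulation gave −0.011, −0.020, −0.029 SD.
- Standard error at 84 per arm: √(2/84) = 0.154 SD unadjusted, and 0.154 × √(1 − 0.6²) = 0.123 SD adjusted for baseline.
- The shift is therefore 8% to 24% of the adjusted standard error. Coverage of a nominal 95% interval would be 94.9% to 94.3%.

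**5. Same rule, activity guidelines.** If the k removed women do not meet the guidelines, the intervention proportion becomes 43/(100 − k): 43.4%, 43.9%, 44.3%. That is 0.4, 0.9 and 1.3 points too high, against a planned difference of 20.

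**6. Which data are exposed.**
- Pregnancy before T1: T1 and T2 surveys and accelerometry, then the infant survey.
- Pregnancy between T1 and T2: T2 and the infant survey.
- Event first reported at T1: T2 and the infant survey.
- Event first reported at T2: at most the infant survey, which Section 4 says may coincide with T2 for some women.
- Section 5c allows access to infant records, partly to "monitor adverse events and safety outcomes", so an infant's event could come to light before a survey does.

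**The case against.** The strongest reply is that the plan gives a general schedule and then names exceptions in answer to separate prompts. That is ordinary drafting. A reader might infer that the two rules flatly contradict the schedule, but the documents do not support that: a schedule for each woman can coexist with stated grounds for removal. What survives is narrower. The exceptions do not say what they end, and the form's own question about leaving the intervention while data collection continues is not answered for these women.

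A second reply is that ending follow-up at a new pregnancy may be deliberate, since the aims concern postpartum activity and postpartum depression. That is a fair reason to state how such measurements will be used. The protocol does not give it as the reason, and it is a weaker reason for not collecting them.

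A third is size. Section 14 does not anticipate serious events, the pregnancy rule is neutral between arms, and the 16% allowance is not said to exclude withdrawals. All of this stands and limits the severity.

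A reader might also infer that every data source is cut off. The bar on later health information is written for women who withdraw their authorization. No section extends it to women removed under these two rules, or expressly stops record capture for them.

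**Conclusion.** The point holds as a minor one. Two rules end study participation after post-randomization events without saying whether outcome collection continues. Applied as written, they give up T1 or T2 outcomes that could have been obtained, including in usual-care women and in women past the treatment period.

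The expected size is small: about 0 bias from equal pregnancy removal with unaffected outcomes; about 0.01 to 0.03 SD on T2 PHQ-8 if 1 to 3 intervention women who are 1 SD worse are removed; and a detectable difference of 0.435 SD that is unchanged, or rises to about 0.449 SD if 5 to 6 per arm are lost beyond the allowance. The counts, the 1 SD and the 0.6 correlation are assumptions. Unequal removal, or outcomes that differ by arm among removed women, would not cancel.

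It would be tempting to conclude that the rules materially bias the trial or leave it underpowered. The documents give no rates that would support this, and the illustrative figures point the other way. The case for acting is that the loss is avoidable, may be uneven between arms, and cannot be repaired at analysis.

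**What to change.** Amend the withdrawal text in Section 9a and the removal text in Section 14 so that stopping the intervention and stopping follow-up are separate. When the intervention should stop is a clinical decision and is not addressed here. Align both with the schedule and duration of participation in Section 9a.

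State that:
- PHQ-8, survey and record-based outcomes continue in every randomized woman unless she withdraws authorization;
- all women are analysed in the arm to which they were randomized;
- moderate-to-vigorous activity and PHQ-8 measured during a new pregnancy are handled by a rule set in advance, for example used as measured in the main analysis and excluded in a sensitivity analysis.

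The cost is a short amendment with matching consent wording and slightly more follow-up work. No visits are added, because follow-up is by online survey, mailed monitor and health record.

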**Statistical Analysis:**

Primary analyses will include estimation of mean minutes of moderate/vigorous physical activity and mean PHQ-8 depression screening score at each point in time stratified by treatment arm. Patterns in the group differences across time will be noted, and the results of these time-stratified analyses will be synthesized via linear regression models with parameter estimation via generalized estimating equations (GEE) for each outcome separately. GEE accommodates the within-patient correlation in repeated measures to obtain valid estimates of intervention effects and associated standard errors. In addition to study arm and time (categorical variable), model covariates will include those used in the randomization procedure (KP clinic, race/ethnicity, age, parity, marital status, education). In addition, this a priori specified set of model covariates will include baseline depression score and household income as main effects in regression models given their strong association with the outcome; inclusion of such covariates can improve statistical power and precision. Heterogeneity in effect by time since baseline will be assessed by including a treatment by time interaction term.

The approach to analysis of additional continuous outcomes (sleep, stress, anxiety symptoms, maternal infant bonding, infant development) will utilize multivariable linear regression analysis, with the approach to estimation (GEE), inclusion of model covariates, and examining of heterogeneity in treatment effect over time as described above.

The approach to analysis of additional categorical outcomes (meeting PA guidelines, depression diagnosis, anxiety diagnosis) will utilize multivariable log-binomial regression analysis, with the approach to estimation (GEE), inclusion of model covariates, and

examining of heterogeneity in treatment effect over time as described above. We propose the log binomial regression model for point and interval estimation of relative risks (ratio of proportions) rather than the logistic regression model for estimation of odds ratios, for ease in interpretation and avoidance of odds ratio misinterpretation given the relatively high expected frequency of these outcomes.

Sensitivity analyses will examine inclusion of additional covariates in our estimation of treatment effect, with a focus on variables with chance imbalance in distributions by treatment group (determined in preliminary analyses). Analyses resulting in an appreciable change in the estimate of treatment differences or increase in the precision of the treatment effect will be noted.

- When applicable, the power analysis.

We will recruit 200 women (100 per group). For depressive symptoms, the minimum-detectable difference between groups is in the “small” to “medium” effect range of .43 standard deviation units (two-sided test,  $\alpha=.05$ ). For analyses of meeting PA guidelines, we will have sufficient power (.80) to detect a 20 point difference as based on the literature between the MomZing intervention (43%) and control group (23%), allowing for up to a 16% loss-to-follow-up (which is similar to that of previous lifestyle intervention studies at KPNC).

- Any procedures that will be used for quality control of collected data.

The programmer and study investigators will follow standard data management procedures to ensure the quality of the data. The programmer will draw from shared resources of the programmer group, which include detailed documentation about data sources and characteristics, shared programming code to prepare datasets according to standardized parameters, and consultation with other programmers to ascertain best practices based on procedures developed in earlier projects. There will be systematic data checks by assessing the presence of outliers and missing values and calculating the distributions of variables over time periods, medical facilities, demographic subgroups, and other categories. The study team will also compare these results to expectations based on other comparison data or studies, and further investigate possible reasons for any data anomalies. They will develop procedures to address data irregularities, such as by cleaning the data, augmenting the data with other relevant variables, or using analytic techniques to reduce as much as possible the impact of bias in the data.

c. Sharing of Results with Subjects

Describe whether results (study results or individual subject results, such as results of standard or research lab tests and genetic tests) will be shared with subjects or their providers and under which circumstances.

Individual results will not be shared with subjects or their providers but for those who want them, the study results, once published, will be made available.

If the study carries a risk of incidental findings, describe your plan for evaluating these and determining whether and how subjects or their providers will be given this information.

N/A

If laboratory results will be shared with subjects or their healthcare providers, verify that the laboratory conducting the test is Clinical Laboratory Improvement Amendments (CLIA) certified.

N/A

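### The plan rests the validity of its GEE estimates on correlation handling alone, and leaves missing-data method, working correlation and dropout sensitivity analysis unstated despite an allowance of up to 16% loss

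*Combined protocol and SAP*

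**What the plan says.** Section 9.b, Statistical Analysis, begins the primary analysis with arm-specific means of MVPA minutes and PHQ-8 at each time point. It then combines them through "linear regression models with parameter estimation via generalized estimating equations (GEE) for each outcome separately". The justification is that "GEE accommodates the within-patient correlation in repeated measures to obtain valid estimates of intervention effects and associated standard errors". Covariates are the randomization factors, baseline depression score and household income. Baseline physical activity is not named. An arm-by-time term is used to look for heterogeneity over time.

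The power paragraph states that "we will have sufficient power (.80) to detect a 20 point difference", "allowing for up to a 16% loss-to-follow-up". Loss to follow-up is mentioned only there. The planned sensitivity analyses add covariates. The quality-control paragraph says missing values will be checked and that unspecified analytic techniques may be used to limit bias. The plan gives no working correlation, weighting, imputation, likelihood-based model, missing-data assumption or not-at-random analysis.

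**The concern.** With T1 and T2 outcomes, a woman's T1 PHQ-8 or activity may influence whether she supplies T2 data. GEE with working independence estimates the T2 contrast from T2 completers and borrows nothing from the T1 values of women who left. If the T1-to-dropout relation differs by arm, completers are selected differently in each arm and the T2 difference shifts.

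Such a difference is plausible here. Section 9.a says participants cannot be blinded. Only one arm has a program to abandon. Section 14 removes women with serious exercise-related adverse events, and Section 15 lists exercise injury as a risk of the intervention group. At stake is the size of the primary effect, with no planned analysis that would reveal the problem.

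**Working it through.** **Inputs from Section 9.b:** 100 women per arm, two-sided alpha .05, up to 16% loss, 43% vs 23% meeting activity guidelines at power .80, and a minimum detectable difference of .43 SD for depressive symptoms. Power .80 for the .43 SD figure is assumed.

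**Step 1, the plan's own figures.** Retained per arm: 100 × (1 − .16) = 84.
- Depressive symptoms: (1.960 + 0.842) × √(2/84) = .432 SD.
- Activity guidelines, unpooled: SE = √((.43×.57 + .23×.77)/84) = .0709. Then .20/.0709 − 1.960 = 0.861, so power is 80.5%. With pooled variance it is 79.3%.

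Both figures reproduce. The 16% loss is therefore allowed for in sample size, but not in estimation.

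**Step 2, large-sample value of the T2 effect.** No simple formula covers the cases, so I simulated 1,000,000 women per arm. Assumptions not in the documents:
- true effect −0.43 SD at T1 and T2;
- T1 complete, 16% T2 dropout in each arm;
- dropout log-odds changing by 1.0 per SD of T1, measured from the arm mean;
- baseline outcome as a main effect.

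Correlation sets are T0–T1 / T0–T2 / T1–T2. Cells show GEE independence / GEE exchangeable / Gaussian likelihood with the true covariance.

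| Set | Same in both arms | MomZing only | Opposite by arm |
|---|---|---|---|
| .6/.6/.6 | −.431/−.430/−.430 | −.463/−.429/−.429 | −.498/−.429/−.429 |
| .6/.4/.6 | −.434/−.433/−.433 | −.476/−.427/−.419 | −.518/−.420/−.405 |
| .5/.5/.7 | −.431/−.431/−.431 | −.495/−.431/−.431 | −.559/−.431/−.431 |
| .5/.45/.6 | −.431/−.432/−.432 | −.481/−.430/−.428 | −.534/−.429/−.425 |

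In the last two sets the independence error runs from .481 − .43 = .05 to .559 − .43 = .13 SD. In the first two sets, where T0–T1 is .6, it runs from .03 to .09. As constructed (symptomatic women leaving MomZing), it favours the intervention; the reverse pattern would understate the effect.

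**Step 3, no baseline value of the outcome in the model,** as the wording leaves MVPA (sign mirrored). Independence GEE gives −.51 to −.53 (MomZing only) and −.60 to −.63 (opposite), an error of about .08 to .20 SD. Exchangeable GEE and likelihood give −.43. The independence figures also describe the raw arm means at T2, if those are computed on observed cases.

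**Step 4, other mechanisms, outcome's baseline included.**
- Dropout driven by baseline, opposite by arm: all three methods within .01 of −.43 in three sets. In the .6/.4/.6 set they give −.38 to −.40.
- Dropout driven by the unseen T2 value, opposite by arm: likelihood gives −.57 to −.60, still off by .14 to .17 SD.
- Weaker slope (0.4 per SD), MomZing only: independence gives −.44 to −.46.

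**Step 5, trial size.** With 100 per arm, correlations .5/.5/.7, about 17% loss, no true effect and 1,500 runs, type I error in the opposite-by-arm case was 19.5% with independence GEE and 6.2% with exchangeable. With the same mechanism in both arms it was 5.6% and 5.1%.

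**The case against.** The strongest reply is that the size depends on working independence, which the plan does not choose. Its sentence about accommodating correlation can be read as pointing to a correlated structure, and exchangeable GEE stays within about .01 SD of the truth in every T1-driven case above. This stands as a limit on the concern. It does not close it: two analysts following Section 9.b could choose either structure and, in the worst case above, work at 19.5% or 6.2% type I error.

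The scenarios are also assumed. The documents give no correlations, no dropout mechanism and no evidence of arm-dependent loss; 16% is a ceiling; opposite directions by arm is a deliberate worst case. This stands too, so the figures show a possible range and not a forecast. An effect pooled over T1 and T2 moves less, because T1 is complete in these scenarios: a separate run with correlations .5/.45/.6 and 16% overall loss gave −.42 to −.46.

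A reader might infer that any dropout related to earlier outcomes invalidates the analysis. The documents do not support that. Baseline PHQ-8 is already a covariate, which largely covers dropout driven by it, and a mechanism common to both arms leaves the arm difference almost unchanged. A reader might also infer that a likelihood model or imputation removes the problem at no cost. It does not: both need missing at random and an adequate model, and Step 4 shows what remains when dropout follows unseen values.

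**Conclusion.** The concern holds in a limited form. The validity statement is incomplete because correlation handling does not address dropout, and nothing else in Section 9.b does. The exposure is specific: T2 loss that depends on T1 outcomes differently by arm, analysed with working independence.

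Under a strong mechanism (1.0 log-odds per SD) and the assumed correlations, the PHQ-8 effect at T2 would be off by about 0.05 to 0.13 SD (0.03 at the lowest), or 12% to 30% of the .43 SD target (.05/.43 and .13/.43). MVPA is more exposed while baseline activity stays out of the model. The error is near zero with a common mechanism or a near-correct working correlation.

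The documents do not show that this trial's estimate is biased, or that GEE is a wrong choice. They show that protection is left to an unstated choice. This should be corrected before analysis, and the correction is cheap.

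**What to change.** In Section 9.b, Statistical Analysis:

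1. State the missing-data assumption, and analyse each continuous primary outcome on all randomized women with a missing-at-random method. One option is a mixed model for repeated measures with unstructured covariance, arm by time and the planned covariates, preferably letting the baseline coefficient differ by visit; a common coefficient is what left the small likelihood error in the .6/.4/.6 set. The other is GEE after multiple imputation by arm that includes T1 outcomes. Imputation also serves the log-binomial outcomes, for which a mixed model is not a direct substitute.
2. If GEE on observed data is kept, specify a non-independence working correlation, for example exchangeable.
3. Add baseline physical activity as a covariate for MVPA.
4. Add one delta-adjusted sensitivity analysis for dropout, since none of these methods removes bias from loss tied to unseen outcomes.
5. Reword the validity sentence so that it names the missing-data condition.

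The cost is plan wording and modest programming, with no new data. The downside is reliance on the missing-at-random and model assumptions, which item 4 is there to probe.
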